9.3 Selection of Study Population

Approximately 1330 subjects with EAD including MCI due to AD and the early stages of mild AD will be enrolled across up to approximately 350 centers worldwide. Randomization will be stratified according to region (7 levels), clinical dementia staging, with no more than approximately 25% of the randomized subjects diagnosed with the early stages of mild dementia due to AD, and concurrent AD medication use.

Subjects who do not meet all of the inclusion criteria or who meet any of the exclusion criteria will not be eligible to receive study drug.

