7. Subjects must have been on stable doses of all other (ie, non-AD related) permitted concomitant medications for at least 4 weeks prior to Randomization, except for medications which are administered as short courses (eg, up to 3 weeks unless discussed and agreed with the Medical Monitor) of treatment (eg, anti-infectives, oral steroids) or which are to be used on a Pro re nata (PRN) basis. Subjects who require a short course of treatment, such as anti-infectives or oral steroids, may be randomized once the acute illness has completely resolved, even if the concomitant medication continues.
8. Must have an identified study partner (defined as a person able to support the subject for the duration of the study and who spends at least 8 hours per week with the subject). The study partner must be literate and able to provide written informed consent. (revised per Amendment 03) In addition, this person must be willing and able to provide follow-up information on the subject throughout the course of the study. This person must, in the opinion of the investigator, spend sufficient time with the subject on a regular basis such that they can reliably fulfill the requirements of being a study partner. A study partner need not be living in the same residence with the subject. For such a study partner not residing with the subject, the investigator has to be satisfied that the subject can contact the study partner readily during the times when the study partner is not with the subject. Study partners need to provide input to the following assessments: CDR, FAQ, EQ-5D, QOL-AD, Zarit's Burden Interview, NPI-10, and the clinical assessment of suicidality. Consideration can occur for the investigator to decide whether the study partner can provide information over the telephone or whether the study partner must attend the study visits in person with the subject.
9. Provide written informed consent. Subjects must, in the investigator's judgment, have the capacity to consent (capacity to consent should be determined in accordance with

applicable professional standards and local laws/regulations). (revised per Amendment 03)

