 - Thyroid stimulating hormone (TSH) above normal range. Other tests of thyroid function with results outside the normal range should only be exclusionary if they are considered clinically significant by the investigator (this applies to all subjects whether or not they are taking thyroid supplements)

- Abnormally low (below LLN) serum Vitamin B12 levels (if subject is taking Vitamin B12 injections, level should be at or above the LLN)

10. Subjects at risk of increased risk of infection, specifically:

- Subjects with chronic viral hepatitis. Subjects with a history of chronic viral hepatitis C may be included if they meet the following requirements:
 - 1) evidence of treatment with direct antiviral combination therapy
 - 2) evidence of sustained virological response at least 12 weeks post-treatment

The inclusion of subjects with a history of chronic viral hepatitis C must be discussed and agreed with the Medical Monitor. (revised per Amendment 03)

- A history of active tuberculosis disease (TB), a history of ophthalmic shingles or a history of ocular herpes simplex virus (HSV) infection (revised per Amendment 03)
- Any active infection within the last 4 weeks before randomization. For such cases, the timing of randomization can be extended (up to 4 weeks) to allow the infection to resolve
- Any immunological disease which is not adequately controlled, or which requires treatment with biologic drugs during the study. History of immunoglobulin deficiency or other immunodeficiency disorders (including subjects known to be HIV positive)

11. Have received any live/live attenuated vaccine in the 3 months before randomization

12. Any chronic inflammatory disease that is not adequately controlled or that requires systemic immunosuppressive or immunomodulatory therapy. (revised per Amendment 03)

NOTE: The following subjects do not need to be excluded:

- Subjects with seasonal or perennial allergic rhinitis, asthma, or chronic obstructive pulmonary disease where the condition is considered to be stable and adequately controlled by inhaled steroids.
- Hashimoto's thyroiditis but who are stable on thyroid replacement therapy and not on systemic immunosuppressive therapy.
- Cutaneous manifestations of immunological disease that do not require systemic immunosuppressive therapy or systemic immunomodulatory therapy (ie, topical steroid treatment is permitted)

13. Any other clinically significant abnormalities, such as:

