- Physical examination or vital signs at Screening or Baseline that in the opinion of the investigator require further investigation or treatment or may interfere with study procedures or safety. (revised per Amendment 03)
 - Laboratory tests or ECG at Screening that in the opinion of the investigator require further investigation or treatment or may interfere with study procedures or safety. (revised per Amendment 03)
 - Other medical conditions (eg, cardiac, respiratory, gastrointestinal, psychiatric, renal disease) which are not adequately and stably controlled, or which in the opinion of the investigator(s) could affect the subject's safety or interfere with the study assessments (revised per Amendment 01)
 - Illiteracy, or severe visual or hearing impairment that would prevent the subject from performing psychometric tests accurately
14. A prolonged QTc interval calculated using Fridericia's formula (QTcF) interval (QTcF greater than 450 ms according to central reading at Screening). (revised per Amendment 03) If the QTcF is greater than 450 ms on the first single 12-lead ECG, 2 additional 12-lead ECGs will be performed 1 minute apart and the mean of the 3 QTcF values will be calculated.
15. Malignant neoplasms within 5 years of Screening (except for basal or squamous cell carcinoma in situ of the skin, or localized prostate cancer in male subjects with treatment cycles completed at least 6 months prior to screening). Subjects who had malignant neoplasms but who have had at least 5 years of documented uninterrupted remission before Screening need not be excluded.
16. Hypopigmentation conditions (eg, albinism and vitiligo). Hypopigmentation associated with scarring need not be exclusionary
17. Known or suspected history of drug or alcohol abuse or dependence within 2 years before Screening
18. Taking prohibited medications
19. Have participated in a clinical study involving:
- any therapeutic monoclonal antibody, protein derived from a monoclonal antibody, immunoglobulin therapy, or vaccine within 6 months before Screening for whom it cannot be documented that they were randomized only to placebo or never received study drug
 - elenbecestat (E2609)
 - any new chemical entity for AD with last study drug dose occurring within 6 months prior to Screening unless it can be documented that the subject received only placebo

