9.4.7 Prior and Concomitant Therapy

Any medication (including over-the-counter medications) or therapy administered to the subject prior to the study (within 6 months of randomization) and during the study (starting at the date of informed consent) will be recorded on the Prior & Concomitant Medication eCRF or Non-Pharmacological Procedures eCRF. The investigator will record on the Adverse Event eCRF any AE for which the concomitant medication/therapy was administered. If the concomitant medication/therapy is being administered for a medical condition present at the time of entry into the study, the investigator will record the medical condition on the Medical History and Current Medical Condition eCRF.

Listings of prohibited and permitted drugs are provided in [Appendix 2](#) (Prohibited medications are presented in [Listing 1](#), [Listing 2](#), and [Listing 3](#). Medications that are permitted with restrictions are listed in [Listing 4](#), [Listing 5](#), and [Listing 6](#)).

The following agents are not permitted before randomization (specific time frames are shown below) and until the last visit during the treatment period: (revised per Amendment 01)

- a) Immunoglobulin therapy and biologic drugs are not permitted within 6 months before Screening and until the last visit during the treatment period (revised per Amendment 01)
- b) Systemic immunosuppressive or immunomodulatory drugs are not permitted for a period of 5 half-lives or 60 days (whichever is longer) before randomization and until the last visit during the treatment period (revised per Amendments 01 and 03)
- c) Moderate to strong inhibitors of carboxylesterase 2 (CES2) enzyme activity are not permitted for a period of 5 half-lives or 7 days (whichever is longer) before randomization and until the last treatment visit. Simvastatin use is permitted only with QD evening administration.
- d) Live/live attenuated vaccines are not permitted within 3 months before randomization and until the last treatment visit (this does not apply to non-live/inactivated vaccines) (revised per Amendment 01)

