Concomitant therapy with AChEI or memantine should only be allowed and/or acceptable for the region or country in which the study is being conducted and should follow the local standard of care for symptomatic treatment (revised per Amendment 01). Subjects who are taking AChEI or memantine will be required to be on a stable dose for at least 12 weeks before randomization. Initiation of therapy or changing dose of AChEIs or memantine during the study should be undertaken in compliance with local standard of care for symptomatic treatment of AD. (revised per Amendment 02). Subjects who start on AChEI or memantine

or change their dose during the Treatment Period will be permitted to continue in the study; however, subjects should not undertake cognitive assessments until they have been on a stable dose for at least 4 weeks.

Subjects who are taking other medications will be required to be on a stable dose for at least 4 weeks before randomization, except for medications which are administered as short courses (eg, up to 3 weeks unless discussed and agreed with the Medical Monitor) of treatment (eg, anti-infectives, oral steroids) or which are to be used on a PRN basis. Concomitant medications (including short-term use of benzodiazepines and opiates) which are used on a PRN basis and which are central nervous system (CNS) active and may affect cognitive function are not permitted during a period of 72 hours prior to cognitive testing. (revised per Amendment 03)

For subjects who undergo an LP for collection of CSF: Subjects who are on anticoagulants may have a variable dose but should have stable anticoagulation control for at least 4 weeks before the LP procedure. Subjects may be required to stop their anticoagulant medication prior to CSF collection and then restart this medication after the LP procedure, as per local guidelines.

Either aspirin or clopidogrel (or any other antiplatelet drug which is not aspirin) is permitted in all subjects. Aspirin and clopidogrel (or any other antiplatelet drug which is not aspirin) in combination are also permitted but subjects who are on such a combination of antiplatelet drugs may be required to stop 1 or more of these antiplatelet drugs before the LP procedure and restart after the LP as per local guidelines.

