Appendix 2 List of Permitted and Prohibited Prior/Concomitant Medications

Prohibited medications are shown in [Listing 1](#), [Listing 2](#), and [Listing 3](#). Medications permitted with restrictions are listed in [Listing 4](#), [Listing 5](#), and [Listing 6](#). These may not be all-inclusive listings. Please contact the medical monitor(s) if the investigators have any questions or concerns regarding any medication not listed that your subjects may be taking before enrollment or start during the course of the E2609-G000-302 study.

Antibiotics, analgesics, and anti-inflammatory drugs intended for short courses of treatment are permitted and do not need to follow the restrictions of [Listing 6](#) for a stable dose of 4 weeks before Baseline. If these medications may affect cognitive function but the medications are clinically indicated, then cognitive testing should not take place until at least 72 hours after the last dose of the course of treatment.

Prohibited Prior/Concomitant Medications

Listing 1 Prohibited Medications Within 5 Half Lives or 7 Days, Whichever is Longer, Before Randomization and Until the Last Visit During the Treatment Period

Moderate to Strong Inhibitors of Carboxylesterase 2 (CES2) Enzyme Activity
Generic name
Loperamide
Orlistat
Telmisartan
Fenofibrate
Carvedilol
Manidipine
Diltiazem
Verapamil
Itraconazole (revised per Amendment 04)

NOTE: Simvastatin use is permitted only with once daily evening administration.

Listing 2 Prohibited Medications Within 5 Half Lives or 60 Days, Whichever is Longer, Before Baseline and Until the Last Visit During the Treatment Period

Systemic Immunosuppressants^a and Immunomodulatory Drugs (revised per Amendments 01 and 03)	
Prednisolone	Deltasone, Prednicot, Prednisone Intensol, Rayos, Sterapred, Sterapred DS
Methylprednisolone	Medrol, Meprolone
Dexamethasone	Decadron, Dexasone, Diodex, Hexadrol, Maxidex
Azathioprine	Azasan, Imur
Mycophenolate	CellCept, Myfortic
Fingolimod	Gilenya
Methotrexate	Trexall
Ciclosporine	Gengraf, Neoral

Prohibited Medications Within 6 Months Before Screening and Until the Last Visit During the Treatment Period (revised per Amendment 01)

Immunoglobulin Therapy and Biologic Drugs (revised per Amendment 01)	
Ranibizumab	Lucentis
Bevacizumab	Avastin
Infliximab	Remicade
Etanercept	Enbrel
Adalimumab	Humira
Omalizumab	Xolair
Efalizumab	Raptiva

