Immune globulin IV, IVIG, IGIV	Carimune, Flebogamma, Gamimune N, Gammagard, Gamunex, Gammar-P IV, Iveegam, Octagam, Panglobulin, Vigam, Polygam S/D, Privigen, Sandoglobulin, Venoglobulin-S
Denosumab	Prolia (revised per Amendment 01)
Other monoclonal antibodies not listed here	

^aTopical, ocular, and inhaled formulations with minimal systemic exposure need not be prohibited. (revised per Amendment 03)

Listing 3 Prohibited Live/Live Attenuated Vaccines Within 3 Months Before Randomization and Until the Last Visit During the Treatment Period (this does not apply to non-live/inactivated vaccines)

Bacterial vaccines	Viral vaccines
Bacillus Calmette-Guérin vaccine against tuberculosis	Measles vaccination
Typhoid vaccination (oral)	Mumps vaccination
Cholera vaccination (oral)	Rubella vaccination
	Oral polio vaccination (Sabin)
	Yellow fever vaccination
	Varicella (chickenpox) vaccination
	Rotavirus vaccination
	Japanese encephalitis vaccination
	Live attenuated influenza vaccine (FluMist in the United States and Canada, and Fluenz in Europe)

This list is not exhaustive

Permitted Prior/Concomitant Medications

Listing 4 Medications Which Need To Be on a Stable Dose for 12 Weeks Before the Cognitive Assessments at Visit 2 and Should Remain on the Same Stable Dose From Visit 2 to Follow Up Visit 15

Cognitive Enhancers	
Donepezil	Aricept
Rivastigmine	Exelon
Galantamine	Reminyl
Memantine	Namenda

Listing 5 Permitted Medications Used on PRN Basis Which Are Not to be Used Within 72 Hours Before Cognitive Testing

Generic name	Trade name
Opiates	
Morphine	Astramorph PF, Avinza, Depo Dur, Duramorph, Infumorph, Kadian, MS Contin, MSIR, Oramorph SR, RMS, Roxanol
Opiate Agonists	
Meperidine	Demerol, Meperitab
Fentanyl	Actiq, Duragesic, Fentora, Onsolis, Sublimaze
Codeine	Codeine
Oxycodone	Dazidox, Endocodone, Eth-OxyDose, OxyContin, OxyFast, OxyIR, Percolone, Roxicodone, Roxicodone Intensol
Other opioids or opioid agonists which are used on PRN basis	
Benzodiazepines (short-term use only, [ie, 2 to 4 weeks]) and sedatives (revised per Amendment 03)	
Estazolam	ProSom
Alprazolam	Alprazolam Intensol, Niravam, Xanax
Triazolam	Halcion
Midazolam	Versed
Lorazepam	Ativan
Flunitrazepam	Rohypnol
Temazepam	Restoril
Clonazepam	Ceberclon, Klonopin
Diazepam	Diastat, Dizac, Valium
Chlordiazepoxide	H-Tran, Librium
Flurazepam	Dalmane
Zopiclone	(various)
Zolpidem	Ambien; others
Ramelteon	Rozerem
Amitriptyline	(various)
Dothiepin	(various)
Risperidone	Risperdal
Olanzapine	Zyprexa

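### Inclusion criterion 7 lets a subject be randomized while a short oral steroid course is still running, but Section 9.4.7(b), Listing 2 and exclusion 18 bar that same subject

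*Protocol*

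**What the plan says.** **The permission.** Inclusion criterion 7 (Section 9.3.1) requires stable doses of permitted non-AD medications for 4 weeks before randomization. It exempts short courses and gives oral steroids as an example. A second sentence adds that subjects needing a short course of treatment such as "oral steroids, may be randomized once the acute illness has completely resolved, even if the concomitant medication continues". Section 9.4.7 repeats the example when it exempts "short courses (eg, up to 3 weeks unless discussed and agreed with the Medical Monitor) of treatment (eg, anti-infectives, oral steroids" from the 4-week stable-dose rule.

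**The bar.** Section 9.4.7, item b, states: "Systemic immunosuppressive or immunomodulatory drugs are not permitted for a period of 5 half-lives or 60 days (whichever is longer) before randomization". The prohibition then runs to the last visit of the treatment period. Listing 2 in Appendix 2 is headed "Prohibited Medications Within 5 Half Lives or 60 Days, Whichever is Longer, Before Baseline" and names prednisolone, methylprednisolone and dexamethasone. Its footnote lists the forms let through: topical, "ocular, and inhaled formulations with minimal systemic exposure need not be prohibited". Oral courses, short or long, are not among them.

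**The link to eligibility.** Exclusion 18 (Section 9.3.2) reads "Taking prohibited medications". Section 9.3 says that subjects "who meet any of the exclusion criteria will not be eligible to receive study drug".

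Version 3.0, included in the same file, carries the same permission and the same 60-day bar in its synopsis and body.

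**The concern.** Criterion 7 gives a site an express permission and names the drug class. The bar has to be put together from Section 9.4.7(b), an appendix listing, its footnote and exclusion 18. A coordinator working from the inclusion criteria alone would randomize a subject whom the rest of the protocol excludes. That subject would take the first dose of study drug on a prohibited systemic immunosuppressant, which is both an eligibility deviation and use of a prohibited drug.

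The bar has a safety purpose in this trial. Section 7.1 reports some reduction in CD4 counts at 50 to 100 mg by Day 15 of the multiple-dose study, and the dose here is 50 mg. Exclusion 9 screens on absolute lymphocyte count, and Section 9.3.3 interrupts dosing on a confirmed count below 800/mm³. The protocol does not say what a short steroid course does to that count, so the size of any safety effect cannot be stated from the document. With up to approximately 350 sites (Section 6), different sites reading the text differently is foreseeable.

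**Working it through.** There is no power or alpha figure to reproduce. The check sets the rules side by side and compares washout times.

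**Inputs**
- Required washout W: the longer of 5 half-lives or 60 days (Section 9.4.7(b), Listing 2). Half-lives are not given, so W is at least 60 days.
- Washout at randomization under criterion 7 when the drug is still being taken: 0 days.
- Example length of a short course: 3 weeks = 3 × 7 = 21 days (criterion 7, Section 9.4.7).
- Longest prerandomization phase: 50 + 30 = 80 days (Section 9.1.1).

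**Step 1: can one subject satisfy both rules?** Take a subject on oral prednisolone whose acute illness has resolved and whose course is still running at Visit 2.
- Criterion 7: may be randomized.
- Section 9.4.7(b) and Listing 2: washout is 0 days against at least 60, a shortfall of at least 60 − 0 = 60 days. Use beyond the first dose also breaks the on-treatment part of the bar.
- Listing 2 footnote: does not apply, because the drug is oral.
- Exclusion 18: met, because the subject is taking a prohibited drug.
- Section 9.3: one exclusion is enough, so the subject is ineligible.

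The answers conflict, and no form of the permission survives for a Listing 2 steroid still being taken. The permission remains sound for anti-infectives.

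**Step 2: does other text supply the missing exemption?**
- The short-course sentence in Section 9.4.7 qualifies the 4-week stable-dose rule, not item b.
- The preamble to Appendix 2 says short courses of anti-inflammatory drugs are permitted. The restriction it expressly lifts is that of Listing 6 (stable dose); it names neither steroids nor Listing 2.

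**Step 3: was the rule reviewed?** Compared with Version 3.0, the Amendment 03 text no longer bars ocular immunosuppressants in item b, and it adds ocular forms to the Listing 2 footnote. So this rule was edited, and the conflict over short oral courses was left in place.

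**Step 4: what would enforcing the bar cost a subject?** A full 21-day course begun on the day of consent, plus 60 days off drug, ends on day 21 + 60 = 81, one day past the 80-day maximum, so that subject would need rescreening. A 7-day course (assumed for illustration) ends on day 7 + 60 = 67 and fits as a delay. Screening MRI and CSF results stay valid for 90 days, including under a new screening number (Sections 9.1.1.1.4 and 9.1.1.1.5).

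**The case against.** The strongest reply is that the sponsor meant short courses to be an exception. Criterion 7, Section 9.4.7 (the section that also holds item b) and the Appendix 2 preamble all speak of short courses as acceptable. Exclusion 12 is aimed at chronic inflammatory disease needing systemic immunosuppression, not at a brief course for an acute illness. Against that, the first sentence of criterion 7 is limited to permitted medications, which could be read as leaving Listing 2 drugs out. Both readings are arguable, and what stands is that the intent is open. A reader might infer that the exclusion simply governs and that criterion 7 is the provision in error. The documents support only that the texts conflict and that, as written, a subject still on the drug is excluded. They do not show which text the sponsor would keep.

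Two further inferences go too far:
- **A steroid already stopped.** Exclusion 18 is worded in the present tense, and the 60-day washout stands in Section 9.4.7, not in the exclusion list. A subject who stopped recently breaches Section 9.4.7(b) but is not plainly caught by exclusion 18. Nor does criterion 7's allowance for continuing medication create that case.
- **A fixed shortfall after an infection.** Exclusion 10 covers "Any active infection within the last 4 weeks before randomization", that is 4 × 7 = 28 days. A course of the example length, 21 days, begun during the infection would have ended before those 28 days had passed. Reaching Visit 2 on the drug would take a longer course, agreed with the Medical Monitor. No infection-specific figure follows from criterion 7 in the ordinary case.

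Safeguards also exist: lymphocyte screening, hematology at every visit, and the interruption rule. They limit harm but do not settle who is eligible.

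**Conclusion.** The contradiction holds in the Amendment 03 text shown, and in Version 3.0 before it. For a subject still taking a Listing 2 steroid at randomization, criterion 7 says yes, and Section 9.4.7(b), Listing 2 and exclusion 18 together say no, with 0 days of washout against at least 60. It should be fixed, because following one eligibility criterion literally puts an ineligible subject on study drug.

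The consequence is confined to eligibility, deviations and safety oversight. Power, alpha and the primary analysis are unaffected, and the number of subjects concerned is unknown. The conclusion assumes that the oral steroid is one covered by item b or Listing 2 and that no later version has corrected the text. Later versions, if any, are not shown, and a few entries in Appendix 2 carry an Amendment 04 tag.

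**What to change.** Delete oral steroids from both places in criterion 7, from the short-course example in Section 9.4.7, and from the matching synopsis text (inclusion criterion 7 and Concomitant Drug/Therapy in the Version 3.0 synopsis; the later synopsis eligibility text is not shown). Eligibility then agrees with the immunosuppressant bar. The downside is that a few subjects are delayed or rescreened.

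If the sponsor did intend to allow short courses, write that instead: an explicit, time-limited exemption in Section 9.4.7(b) and Listing 2, for example up to 3 weeks, the figure already in criterion 7. The downside is that some subjects would start study drug during systemic immunosuppression.

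Either way the cost is a wording amendment and a letter to up to approximately 350 sites, with authority and IRB/IEC approval where Section 11.1 requires it. Issue it while enrolment is open. It should not wait for the Extension Phase amendment (Section 9.1.3), which has no date and concerns subjects who have completed 24 months of treatment, so it could arrive after the last subject is randomized.
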